--	--

	
Participants can also roll over into Stage 2 via two pathways:
 
• Stage 1 participant rolls over to Stage 2• Stage 2 participant rolls over to a different Stage 2 treatment arm 
Participants will be allocated to 1 of 3 cohorts based on their IS regimens:
 
• Cohort D: Receipt of MMF or MPA• Cohort E: Receipt of MTX• Cohort F: Receipt of any BCDT within the past 18 months. 
Treatment Arms: Participants in Cohorts D, E, and F will receive a dose of an alternative COVID-19 vaccine compared to their previous COVID-19 vaccine doses. Originally, participants who previously received 3 total doses of a single mRNA vaccine (Moderna COVID-19 Vaccine OR Pfizer-BioNTech COVID-19 Vaccine) received their choice of either the Janssen vector-based COVID-19 vaccine or the other mRNA COVID-19 vaccine, and participants who previously received 2 doses of the Janssen vector-based COVID-19 vaccine received the Moderna COVID-19 Vaccine.
 
Update: Beginning with v4.0 of the protocol, this trial will not utilize the Janssen vector-based COVID-19 vaccine. Participants who previously received 3 total doses of a single mRNA vaccine will receive their choice of an alternative mRNA COVID-19 vaccine or the Sanofi-GSK protein-based COVID-19 vaccine. Participants who previously received 4 or more doses of a single mRNA vaccine or 3 or more doses of a mixture mRNA vaccines (Moderna COVID-19 Vaccine AND Pfizer-BioNTech COVID-19 Vaccine, in any order or combination) will receive the Sanofi-GSK protein-based COVID-19 vaccine. Beginning with v6.0 of the protocol, bivalent versions of the mRNA vaccines, Moderna and Pfizer-BioNTech COVID-19 vaccines, replaced original monovalent versions.
 
Participants in Cohorts D and E will withhold their cohort-defining IS medications before and after the alternative vaccine dose per protocol instructions. Participants in Cohort F who are taking MMF, MPA, or MTX in addition to BCDTs will withhold these medications before and after the alternative vaccine dose per protocol instructions.
 
Schedule of Events: Visits to assess endpoints will occur at Baseline (Week 0), Week 4 ± 1 week, Week 12 ± 2 weeks, Week 24 ± 2 weeks, Week 36 ± 2 weeks, and Week 48 ± 2 weeks. A participant who is newly recruited to the study for entry into Stage 2 may be on study for up to a maximum of 13 months. A participant who enters Stage 2 after a serologic negative, suboptimal, or low immune response to their Stage 1 vaccine dose may be on study for up to a maximum of 26 months. Rollover participants will discontinue follow-up as part of Stage 1 upon rollover into Stage 2. A participant who rolls over to a different Stage 2 treatment arm 2 after a serologic negative, suboptimal, or low immune response to another Stage 2 vaccine dose may be on study for up to a maximum of 38 months.
 
Pediatric Population
 
Pediatric Stage 1:

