--	--

	
to the study for entry into Stage 2 may be on study for up to a maximum of 13 months.
 
Adaptive Design
 
An adaptive design will be employed such that cohorts and arms defined by additional vaccine doses and IS treatment plans may be added or modified based on emerging data from existing and new FDA Emergency Use Authorization (EUA) or approvals of COVID-19 vaccines:
 
• New cohorts may be defined based on changes in the medication groups if it becomes obvious that certain medications are highly associated with suboptimal or low immune response to initial COVID-19 vaccine regimen.• Cohorts may limit or expand the autoimmune diseases that are eligible to be included in the clinical trial, and may include expansion cohorts of underrepresented diseases.• New cohorts may include participants whose antibody response falls to suboptimal or low immune response levels over time.• Based upon timing of the FDA EUA authorization for children of each of the COVID-19 vaccines used in this trial, the age range of the inclusion criteria may be expanded.• Allocation or randomization to treatment with new COVID-19 vaccines may be incorporated into the design when the products become available.• Identification of additional strategies to enhance vaccine responsiveness in autoimmune diseases, including a temporary switch of immunomodulatory medications.
Primary Endpoint	The primary endpoint in the adult and pediatric populations of a protective antibody response at Week 4 will be assessed by the NIAID-VRC MSD 3 plex (Wu-1 full-length spike, RBD, and N proteins) assay.
Secondary and Exploratory Endpoints	
Secondary Endpoints
 
Secondary endpoints related to antibody response will primarily be assessed by the NIAID-VRC MSD 3 plex (Wu-1 full-length spike, RBD, and N proteins) assay; where applicable, they will also be assessed by the Roche Elecsys® Anti-SARS-CoV-2 S electrochemiluminescence immunoassay.
 
The secondary endpoints are applicable to both the adult and pediatric populations.
 
• Seroconversion at Week 4 following additional doses of COVID-19 vaccine in the subgroup of participants that are anti-COVID-19 antibody negative at Week 0.• Fold increase in anti-COVID-19 antibody levels at Week 4 following an additional dose of COVID-19 vaccine in the subgroup of participants who are anti-COVID-19 antibody positive at Week 0.

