	
the criteria for (re-)entering Adult Stage 2 will be assessed in rollover participants at the time of screening for Stage 2.
 
Individuals who meet all of the following criteria are eligible to (re-)enter Adult Stage 2:
 
4. Received an additional COVID-19 vaccine dose that was completed at least 4 weeks prior and no more than 48 weeks prior to the Stage 2 vaccination.5. Negative or suboptimal serologic response to a previous COVID-19 vaccine administration in one of the qualifying regimens, defined as an Elecsys® Anti-SARS-CoV-2 S (RBD) negative result or positive result of ≤ 200 U/mL, or a low immune response defined as an Elecsys® Anti-SARS-CoV-2 S (RBD) result of ≤ 2500 U/mL, within 4 weeks of the Stage 2 Baseline/Week 0 visit. 
The regimens of COVID-19 vaccination that qualify are as follows:
 
a. 3 doses of the Pfizer-BioNTech COVID-19 Vaccineb. 3 doses of the Moderna COVID-19 Vaccinec. 2 doses of the Janssen COVID-19 Vaccined. 4 doses of a combination of mRNA vaccines (i.e., Pfizer-BioNTech COVID-19 Vaccine, Moderna COVID-19 Vaccine) 
6. Must be currently taking one of the following IS medications with or without additional disease-related medications: MMF (minimum of 1000 mg per day)/MPA (minimum of 720 mg per day), MTX (minimum of 7.5 mg per week), or B cell depleting agents within the past 18 months (such as rituximab, ocrelizumab, ofatumumab).
a. If taking MMF/MPA or MTX, the participant must have initiated therapy at least 8 weeks prior to allocation and be taking the same medications (regardless of dose) as at the time of the initial COVID-19 vaccine regimen. Note: Participants who withheld their IS medications around their initial vaccinations are eligible to participate.b. If enrolling in the BCDT cohort, the participant must have received an anti-CD20 or an anti-CD19 BCDT in the past 18 months.7. No changes in background IS medications, including MMF/MPA or MTX, in the 4 weeks prior to Stage 2 Baseline/Week 0 visit, excluding the following:
a. HCQ,b. Intraarticular steroids,c. The addition of prednisone at ≤ 10mg per day or prednisone at any dose when given for ≤ 3 days, andd. Corticosteroid bursts for non-autoimmune disease-related conditions, such as asthma or COPD, are permitted.
--	---

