Data observations presented in the paper suggest that using 50 U/ml is a reasonable threshold for defining a subgroup of patients who may benefit the most from an additional dose. This threshold is the same as chosen for the companion National Institute of Allergy and Infectious Disease (NIAID)-supported study in solid organ transplantation (COVID19-TB-02). Additional studies in healthy populations have shown average responses to primary vaccination ranging from 2,079 U/ml to 4,435 U/ml, and the reported ranges of immune response were all >250 U/ml [28-30]. Only autoimmune disease patients with a negative or suboptimal serologic response to initial COVID-19 vaccine regimen, defined as an Elecsys® Anti-SARS-CoV-2 S result \leq 200 U/mL at the Screening visit will be eligible to be included in this trial. The trial will also investigate whether transiently withholding IS therapies has an impact on vaccine response. The study will address important public health issues by determining which patients with autoimmune diseases are at increased risk for suboptimal responses to COVID-19 vaccines and identifying safe and effective strategies to enhance their immune response to COVID-19 vaccines. The planned mechanistic studies will provide critical information about the efficacy of an additional homologous vaccine dose in autoimmune patients on other components of immune response such as B and T cell responses, and whether baseline molecular signatures may predict response.

The NIAID ACE Network includes nine institutions with large autoimmune disease patient cohorts, strong infrastructures for autoimmune disease vaccine clinical trials, talented basic immunologists at the forefront of understanding vaccine immune responses, cutting-edge immune-based technologies, and a history of collaborating on projects that transcend the expertise and capabilities of any single center.

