4.2.1 Inclusion and Exclusion Criteria for Adult Participants

4.2.1.1 Inclusion and Exclusion Criteria for Adult Stage 1

4.2.1.1.1 Inclusion Criteria for Adult Stage 1

Individuals who meet all of the following criteria are eligible for randomization/allocation as study participants in Adult Stage 1:

1. Individuals 18 years of age or older that meet classification criteria for SLE, SSc, RA, MS, or pemphigus.
2. Participants must meet the 2019 American College of Rheumatology/European League Against Rheumatism (ACR/EULAR) [2] or 2012 Systemic Lupus International Collaborating Clinics (SLICC) classification criteria for SLE [3], the 2010 ACR/EULAR classification criteria for RA [4], the 2013 EULAR/ACR classification criteria for SSc [5], the 2017 McDonald [6] criteria for MS, and the international consensus criteria for pemphigus [7].
 - a. If a participant has been diagnosed with more than one autoimmune disease, the participant will be assessed based on the disease that is selected for study entry.
3. Willing and able to sign informed consent.
4. Documented full COVID-19 vaccination (CDC card or documentation in medical records) that was completed at least 4 weeks prior and no more than 52 weeks prior to the Screening visit.
5. Negative or suboptimal serologic response to initial COVID-19 vaccine regimen, defined as an Elecsys® Anti-SARS-CoV-2 S result ≤ 200 U/mL, at Screening visit.
 - a. Initial COVID-19 vaccine regimen is defined as either:
 - i. 2 doses of the Pfizer-BioNTech COVID-19 Vaccine
 - ii. 2 doses of the Moderna COVID-19 Vaccine
6. Must be currently taking one of the following IS medications with or without additional disease-related medications: MMF (minimum of 1000 mg per day)/MPA (minimum of 720 mg per day), MTX (minimum of 7.5mg per week), or B cell depleting agents within the past 18 months (such as rituximab, ocrelizumab, or ofatumumab).

- a. If taking MMF/MPA or MTX, the participant must have initiated therapy at least 8 weeks prior to randomization and be taking the same medications (regardless of dose) as at the time of the initial COVID-19 vaccine regimen. Note: Participants who withheld their IS medications around their initial vaccinations are eligible to participate.
- b. If enrolling in the BCDT cohort, the participant must have received an anti-CD20 or an anti-CD19 BCDT in the past 18 months.

7. No changes in background IS medications, including MMF/MPA or MTX, in the 4 weeks prior to Screening, excluding the following:

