4.2.1.2.1 Inclusion and Exclusion Criteria for Adult Stage 2 Newly Recruited Participants

4.2.1.2.1.1 Inclusion Criteria for Adult Stage 2 Newly Recruited Participants

Individuals who meet all of the following criteria are eligible for enrollment as participants in Adult Stage 2:

1. Individuals 18 years of age or older that meet classification criteria [1-6] for SLE, SSc, RA, MS, or pemphigus. If a participant has been diagnosed with more than one autoimmune disease, the participant will be assessed based on the disease that is selected for study entry.
2. Willing and able to sign informed consent.
3. Documented full COVID-19 vaccination (CDC card or documentation in medical records).
4. Received an additional COVID-19 vaccine dose (documented by CDC card or in medical records) that was completed at least 4 weeks prior and no more than 48 weeks prior to the Stage 2 Screening visit.
5. Negative or suboptimal serologic response to a previous COVID-19 vaccine administration in one of the qualifying regimens, defined as an Elecsys® Anti-SARS-CoV-2 S (RBD) negative result or positive result of

≤ 200 U/mL, or a low immune response, defined as an Elecsys® Anti-SARS-CoV-2 S (RBD) result of ≤ 2500 U/mL, within 4 weeks of the Stage 2 Baseline/Week 0 visit.

6. The regimens of COVID-19 vaccination that qualify are as follows:
 - a. 3 doses of the Pfizer-BioNTech COVID-19 Vaccine
 - b. 3 doses of the Moderna COVID-19 Vaccine
 - c. 2 doses of the Janssen COVID-19 Vaccine
 - d. 4 or more doses of a single mRNA vaccine (Pfizer-BioNTech COVID-19 Vaccine OR Moderna COVID-19 Vaccine)
 - e. 3 or more doses of a mixture of mRNA vaccines (Pfizer-BioNTech COVID-19 Vaccine OR Moderna COVID-19 Vaccine)
7. Must be currently taking one of the following IS medications with or without additional disease-related medications: MMF (minimum of 1000 mg per day)/MPA (minimum of 720 mg per day), MTX (minimum of 7.5mg per week), or B cell depleting agents within the past 18 months (such as rituximab, ocrelizumab, or ofatumumab).
 - a. If taking MMF/MPA or MTX, the participant must have initiated therapy at least 8 weeks prior to allocation and be taking the same medications (regardless of dose) as at the time of the initial COVID-19 vaccine regimen. Note: Participants who withheld their IS medications around their initial vaccinations are eligible to participate.

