8.2.2.1.2 Pre-Screening for Adult Stage 2 Rollover Participants

Elecsys® Anti-SARS-CoV-2 S assay results for study participants from visits at Week 4 through Week 48 will be reviewed when received by study sites. Participants with a negative, suboptimal, or low immune response at any visit following receipt of the previous COVID-19 vaccine dose will have the data from their last study visit pre-screened to determine if they may qualify for Stage 2.

If a participant pre-screens successfully for Stage 2, the study site will contact the participant to offer them the opportunity to be fully screened for Stage 2.

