6.2. Demographic and Other Baseline Characteristics

Summary descriptive statistics for baseline and demographic characteristics will be reported for all analysis samples by study arm. Characteristics to be summarized include:

- Age, race, ethnicity, sex, body weight at screening, height
- Disease type and duration
- Roche Elecsys® Anti-SARS-CoV-2 S result at screening; both as a continuous variable and categorical: negative (≤ 0.79 U/mL) vs. positive (> 0.79 U/mL); additionally, categorized as ≤ 0.79 U/mL, > 0.79 U/mL through 50 U/mL, > 50 U/mL through 200 U/mL, > 200 U/mL
- History of prior SARS-CoV-2 infection at Screening
- Time (in weeks) from previous vaccine series
- Additional IS medications
- Steroid dose
- For Stage 2: previous vaccine series
- Medication dose for or Cohort A: MMF or MPA and Cohort B: MTX
- For Cohort C and Cohort F: B cell depletion therapy:
 - Type of B cell depletion therapy
 - Time (in weeks) from last dose of b cell depletion therapy to vaccine.
 - CD19+ B cells

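### Entry rests on one current titre taken up to 52 weeks (Stage 1) or 48 weeks (Stage 2) after the last dose, so waned responders can share arms and titre strata with people who never responded, and no specified analysis uses time since dose

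*Protocol*

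**What the plan says.** **Timing of the qualifying titre.** In Adult Stage 1 (Protocol 4.2.1.1.1) the initial vaccination must be one "that was completed at least 4 weeks prior and no more than 52 weeks prior to the Screening visit", and the Elecsys result is taken at Screening. Pediatric Stage 1 has the same 4-to-52-week window. Newly recruited adults in Stage 2 need an additional dose "that was completed at least 4 weeks prior and no more than 48 weeks prior to the Stage 2 Screening visit". For rollovers the additional dose must be "completed at least 4 weeks prior and no more than 48 weeks prior to the Stage 2 vaccination". In Stage 2 and in Pediatric Stage 1 the titre must fall within 4 weeks of Baseline. No early post-dose titre is required, and an earlier adequate titre is not an exclusion.

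**Rollover.** Protocol 8.2.2.1.2 reviews results from Week 4 through Week 48 and pre-screens "Participants with a negative, suboptimal, or low immune response at any visit following receipt of the previous COVID-19 vaccine dose". The Synopsis and Section 3.1.1.2 then describe such a person as "A participant who enters Stage 2 after a serologic negative, suboptimal, or low immune response to their Stage 1 vaccine dose".

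**Waning.** Protocol 3.1.3 (Adaptive Design) lists it as a possible ground for expansion: "New cohorts may include participants whose antibody response falls to suboptimal or low immune response levels over time".

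**Analysis.** Protocol 13.4.2 tests each arm and titre stratum (at or below 200 U/mL; above 200 and up to 2500 U/mL) against 0.25, and repeats the analysis at or below 50 U/mL. The models in 13.4.3 and SAP 8.2.4 adjust for disease type and for antibody negative or positive after the initial regimen. The further covariates in 13.4.4 do not include time since dose. In the SAP, "Time (in weeks) from previous vaccine series" appears only as a baseline characteristic (6.2), and subgroup details are deferred (8.5).

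**The concern.** The hypotheses concern a poor response to a previous dose. A current titre cannot tell a person whose antibody never rose from one whose antibody rose and fell. A participant above the limit at Week 4 of Stage 1 and below it at Week 24 can enter Stage 2 described as having responded poorly to that same dose.

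If waned responders answer a further dose more readily, a stratum can reject 0.25 although the dose does little for people who never responded. Rejection is meant to mark a subpopulation that may warrant further investigation (Protocol 13.6), so the description of that subpopulation matters. The mix may also differ between arms with calendar time and route of entry, which would confound the non-randomised comparisons by vaccine, by immunosuppressive cohort and within Stage 2.

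**Working it through.** **1. The plan's own figure.** Protocol 13.7: 33 evaluable, one-sided exact test, alpha 0.05, null 0.25, true rate 0.5, power at least 90%. The smallest r with P(X ≥ r | n = 33, p = 0.25) ≤ 0.05 is r = 13, since P(X ≥ 12) = 0.0987 and P(X ≥ 13) = 0.0484. Power is P(X ≥ 13 | p = 0.5) = 0.919. The stated figure reproduces. In 13.7 the allowance of 40 per Elecsys subgroup makes 33 the evaluable number per titre stratum, not per 80-person arm.

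**2. Can a responder wane to the limit inside the window?** Protocol 1.2.1 cites healthy "average responses to primary vaccination ranging from 2,079 U/ml to 4,435 U/ml". The documents give no half-life, so 50 and 100 days are assumed, with exponential decay from that level. Weeks to reach a limit = log2(start / limit) × half-life in days / 7.

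| Start (U/mL) | Limit (U/mL) | Half-lives needed | 50 days | 100 days |
|---|---|---|---|---|
| 2,079 | 200 | 3.38 | 24.1 weeks | 48.3 weeks |
| 4,435 | 200 | 4.47 | 31.9 weeks | 63.9 weeks |
| 2,079 | 50 | 5.38 | 38.4 weeks | 76.8 weeks |
| 2,079 | 0.8 | 11.34 | 81.0 weeks | 162.1 weeks |
| 4,435 | 2500 | 0.83 | 5.9 weeks | 11.8 weeks |

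If decay starts only at Week 4, 44 weeks remain to Week 48 and 48 weeks to Week 52. Reaching 200 U/mL by Week 48 then needs a half-life of at most 44/3.38 = 13.0 weeks (from 2,079) or 44/4.47 = 9.8 weeks (from 4,435). By Week 52 the limits are 14.2 and 10.7 weeks. Entry at or below 200 U/mL after waning is therefore possible with a 50-day half-life. With 100 days it falls at or past the edge. A start of 2,079 U/mL meets the 2500 limit without any waning, so it is not evidence of the mechanism.

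**3. Effect on the test.** Let a share w be waned responders with rate p_w and the rest never-responders with rate p_n. The mixed rate is p = (1 − w)p_n + w·p_w, and the stratum rejects with probability P(X ≥ 13 | n = 33, p). All of w, p_n and p_w are assumptions.

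| p_n | p_w | w = 0 | 10% | 20% | 30% |
|---|---|---|---|---|---|
| 0.25 | 0.60 | 0.048 | 0.118 | 0.231 | 0.382 |
| 0.25 | 0.75 | 0.048 | 0.161 | 0.359 | 0.594 |
| 0.25 | 0.90 | 0.048 | 0.213 | 0.500 | 0.777 |
| 0.20 | 0.80 | 0.008 | 0.064 | 0.231 | 0.500 |
| 0.15 | 0.60 | 0.001 | 0.007 | 0.036 | 0.118 |
| 0.15 | 0.90 | 0.001 | 0.022 | 0.161 | 0.476 |

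The effect runs from negligible to large, depending on values that the documents do not supply.

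**The case against.** **Planned analyses already help.** The primary analysis is stratified by current titre and repeated at or below 50 U/mL. Seroconversion is assessed in people antibody-negative at Week 0 (Elecsys below 0.80 U/mL). On the model above, a fall from 2,079 to 0.8 U/mL takes 81 weeks even at 50 days, outside every window. A fall to 50 U/mL takes 38 weeks at 50 days and 77 at 100. This stands: both analyses lean towards people who never responded. Neither covers the main strata, and neither uses time since dose.

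**The label is operational.** Protocol 4.1 defines suboptimal response by the Screening titre, people above 200 U/mL are called low responders, and Section 1.2.2 justifies the 2500 limit by low Omicron neutralisation, which concerns current protection. This stands. A reader might infer that the entry rule contradicts the Adaptive Design list. It does not: that list says such people may form new cohorts and does not require them to be kept apart.

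**The share may be small.** Protocol 1.2.1 cites levels of 8 U/mL on mycophenolate and below 0.4 U/mL after B cell depletion, so healthy starting titres may not apply. This stands as a limit on size.

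**A stricter analysis would cost power.** One could rest every conclusion on people sampled soon after their dose, for example within 12 weeks. The documents give no basis for such a cut. If it halved the evaluable number to 16, the critical value would be 8 (alpha 0.027) and power at 0.5 would be 60% against 92%. This stands, and the proposal below does not go that far.

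**Conclusion.** The point holds as a matter of what the analysed population is and how it is described. The documents show that waned responders can enter and that no specified analysis uses time since dose or a rollover's own earlier Week 4 titre. The single-arm tests against 0.25 and the non-randomised vaccine, cohort and Stage 2 comparisons are exposed. The randomised continue-versus-withhold contrast in Cohorts A and B is balanced in expectation.

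A reader might go further and infer that waned responders are enrolled in number, or that the primary test has an inflated error rate. The documents do not support either. They give no share, response rates or half-life. The exact test is also valid for the population defined by current titre: a rejection produced by a mixture is a correct statement about that mixture. The 23% to 50% rejection range is conditional on a 20% share, a rate of 0.60 to 0.90 in waned responders and exactly 0.25 in the rest. With 0.15 in the rest and 0.60 in waned responders, the figure at 20% is 3.6%. The error would lie in reading the result as an effect in people who never responded. This is a nearly free improvement, not a flaw that invalidates the design.

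**What to change.** Keep eligibility, arms and the primary test unchanged.

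1. **Models.** Add weeks from last vaccine dose as a covariate in the logistic and linear models of Protocol 13.4.3 and 13.4.4 and SAP 8.2.4. SAP 6.2 already summarises time from the previous series; define it explicitly from the last dose.
2. **Supportive table.** For Stage 2 rollovers, report the Week 4 response proportion separately by their own Week 4 Elecsys result after the previous study dose: at or below versus above the entry limit of the stratum in which they are analysed (200 or 2500 U/mL). Use Elecsys for this split because SAP 12 allows that the MSD protective threshold may be unavailable.
3. **Wording.** Describe the primary populations as having a low current titre, and do not claim an effect in non-responders from the pooled strata alone.

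The cost is one more model term, one supportive table with wide intervals and a few sentences. The dose dates and Week 4 Elecsys results are already collected. The table does not help with newly recruited participants, who have no earlier study titre; for them only the covariate applies.
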